### Data Collection:

Cutaneous toxicity will be assessed at baseline, fraction 15 of XRT and 2 - 5 weeks, 7 - 12 weeks, and 12 – 18 months post XRT by objective ultrasound measurements (UTC). Photographs of the treated breast or chest wall as well as the contralateral breast will also be taken. Documentation of the UTC and photographs will be kept in electronic format for reference. For each visit after the baseline (after treatment has begun), cutaneous toxicity will be assessed by a clinician. Participants will be seen by the investigator in follow up at the third and/or fourth visits and at the fifth visit and an investigator dictation will be performed.

Patients who have had a mastectomy and plan for permanent breast reconstructive surgery after radiation will be assessed within one month of their permanent reconstructive surgery and 5 - 7 months following their surgery using the same procedures as described above. It is highly variable as to when reconstruction will occur. If these time points do not fall within the time frame for the regular study visits, additional study visits will be added for these patients.

Participants will also be asked to complete the Multidimensional Fatigue inventory (MFI)[18], the Pittsburgh Sleep Quality Index (PSQI) [19], the perceived stress scale (PSS)[20], the Inventory of Depressive Symptomalogy-Self Reported (IDS-SR)[21], the PROMIS Fatigue Short form [28], the MOS-item Short-Form health survey (SF-36)(25) and the Godin Leisure-Time Exercise Questionnaire (GLTEQ)(26) to assess levels of fatigue, sleep, stress, and depression at the above time points. These surveys take approximately 15 minutes to complete. Patients who are simultaneously enrolled on the Fatique in Breast Cancer Patients Undergoing Treatment (IRB00028295) may have survey visit assessments completed prior to baseline visit, as they are completing the same assessments for both studies. These surveys will be used for data purposes in lieu of having the patient complete the same paperwork twice. At each visit, patients will be asked to rate their fatigue level and breast pain on a scale of 0-10, 0 being none and 10 being extreme. They will be asked to rate how happy they are with the look of their breast on a scale of 0-10, 0 being not happy and 10 very happy. They will be asked to rate how different their radiated breast is from their non-radiated breast on a scale of 0 - 10, 0 being no difference and 10 being completely different. The patient's self-report of fatigue at these visits will be used to assess the grade of their fatigue. In addition, patients will complete the LENT SOMA [27] scale patient questionnaire at all study timepoints to address pain within the breast. The objective LENT SOMA questionnaire Part 3 will be completed by a study clinician or trained nurse at each visit after baseline.

Blood will be drawn under fasting conditions at visits corresponding to cutaneous toxicity assessments. The blood will be analyzed for inflammatory markers (tumor necrosis factor (TNF)-alpha, soluble TNF receptor 2 (sTNFR2), interleukin (IL)-6, IL-1ra, and C - reactive protein (CRP) as well as genetic factors to determine if they are associated with development of cutaneous toxicity.

Information regarding disease characteristics (including stage, tumor size, grade), patient demographics (including age, race, co-morbidities, social history, body mass index), systemic treatment (including hormone therapy, systemic therapy), surgical treatment, radiation treatment, and clinical outcomes (local control, distant metastasis, survival, and treatment complications) will be collected and recorded.

Patients may also be asked to participate in a long term assessment between 1 and 10 years where they will complete the same study procedures as outlined above. Patients will be compensated \$50.00 for completing this visit.

A follow up phone survey will be taken between 18 months and 10 years after treatment. Using the same scales as in the study visits, the patients will be asked to rate their fatigue level, breast pain, how happy they are with the look of their breast and how different their radiated breast is from their non-radiated breast. They will also be asked if they are on any hormonal treatment for breast cancer and if so, the date they started. We will obtain verbal consent for this survey from patients who completed this study before the follow up phone survey was originally approved on 9/24/2013.

Assuming 10% of patients dropout, 53 patients requiring breast only radiation will be enrolled (2-3 patients per month) to yield a total of 50 patients.

An additional 33 patients requiring regional nodal irradiation and breast or chest wall radiation will be enrolled. Assuming 10% of patients dropout, 33 patients of these patients will be enrolled (2-3 patients per month) to yield a total of 30 patients receiving regional nodal irradiation and breast or chest wall radiation.

In patients undergoing regional nodal irradiation, arm measurements will be taken of the ipsilateral and contralateral upper extremity at baseline, 7 - 12 weeks, and 12 – 18 months post XRT by a licensed lymphedema therapist or study staff trained by a licensed lymphedema therapist. These patients will also be assessed for brachial plexopathy using RTOG grading toxicity, LENT/SOMA grading toxicity, and a modified version of a validated questionnaire to assess symptoms of brachial plexopathy at baseline and 7 - 12 weeks, and 12 – 18 months post XRT.[24] If a patient develops RTOG or LENT/SOMA Grade 3 toxicity, an objective measurement (MRI and/or nerve conduction studies) of brachial plexopathy will be employed.

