### 10. Change in Godin Leisure-Time Exercise Questionnaire (GLTEQ) Score

[Time Frame: Baseline, End of Follow Up (Up to 18 months)] [Safety Issue: No]

The GLTEQ is a self-reported questionnaire used to measure usual leisure-time exercise habits during a typical seven day period. A score of 24 or more indicates active and substantial exercise benefits. A score of 23 units or less indicates insufficiently active and less substantial exercise benefits.

11. Change in Lent Soma Scale Patient Questionnaire Score

[Time Frame: Baseline, End of Follow Up (Up to 18 months)] [Safety Issue: No]

The Lent Soma questionnaire is a self-reported measure of pain. Scores range from 0 to 9. The higher the score, the more pain reported.

12. Change in Fatigue Level

[Time Frame: Baseline, End of Follow Up (Up to 18 months)] [Safety Issue: No]

Participants will be asked to rate their fatigue level on a study specific scale from 0 to 10 where 0 represents no fatigue, and 10 represents the most extreme fatigue.

13. Change in Breast Pain Level

[Time Frame: Baseline, End of Follow Up (Up to 18 months)] [Safety Issue: No]

Participants will be asked to rate their breast pain level on a study specific scale from 0 to 10 where 0 represents no pain, and 10 represents the most extreme pain.

14. Change in Breast Appearance Satisfaction Score

[Time Frame: Baseline, End of Follow Up (Up to 18 months)] [Safety Issue: No]

Participants will be asked to rate the look of their breast on a study specific scale from 0 to 10 where 0 represents not happy, and 10 represents very happy.

15. Difference in Radiated Breast Appearance Score

[Time Frame: Baseline, End of Follow Up (Up to 18 months)] [Safety Issue: No]

Participants will be asked to rate how different the look of their radiated breast is compared to their non-radiated breast on a study specific scale from 0 to 10 where 0 represents no difference, and 10 represents completely different.

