**Outcome and definition**

1. Skin Thickening Ratio (STRA) Baseline
2. Skin Thickening Ratio (STRA) at 1 year
3. Change in Skin Thickening Ratio (STRA) from Baseline to 1 year
4. Overall Survival was defined as months from the date of radiation ended to death or last seen at Emory.
5. Local Recurrence-free Survival (LRFS) was defined as months from the date of radiation ended to local recurrence or last seen at Emory.
6. Distant Recurrence-free Survival (DRFS) was defined as months from the date of radiation ended to distant recurrence or last seen at Emory.

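### One-year skin, pain and appearance results mix surgery with radiotherapy in patients reconstructed before the 12–18 month assessment, and the SAP has no rule for this

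*Protocol*

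**What the plan says.** The Data Collection section of the Protocol schedules ultrasound skin measurement at baseline, at fraction 15, and at 2–5 weeks, 7–12 weeks and 12–18 months after radiotherapy (XRT). A separate paragraph covers mastectomy patients who intend to have permanent reconstruction once radiotherapy is over. Such patients "will be assessed within one month of their permanent reconstructive surgery and 5 - 7 months following their surgery", and the assessments are the same as at the regular visits. On timing it says "It is highly variable as to when reconstruction will occur", and on overlap with the regular visits, "If these time points do not fall within the time frame for the regular study visits, additional study visits will be added for these patients".

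Under Secondary Outcome Measures, items 13 to 15 follow breast pain, satisfaction with appearance and difference from the other breast, from baseline to as late as 18 months. Item 14 reads in part: "Participants will be asked to rate the look of their breast on a study specific scale from 0 to 10".

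The SAP (Outcome and definition) lists STRA at baseline, STRA at 1 year, and "Change in Skin Thickening Ratio (STRA) from Baseline to 1 year". Its Data section gives 75 cases and no exclusions. Its Statistical Analysis section describes summary statistics, univariate tests and a linear regression whose covariates are chosen by univariate significance. Reconstruction appears nowhere in the SAP.

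**The concern.** This is a single-group study. With no control arm, the change from baseline is the only basis for saying what the 15-fraction regimen does to skin and appearance over time. Permanent reconstruction is a second operation on the same site, between baseline and the late measurement. It can move skin thickness and pain in either direction, and it changes the very thing that the appearance items ask about.

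The plan foresees this operation and collects data around it, but does not say how those data enter the late results. Elsewhere it does separate the two causes. For lymphedema (Patients Requiring Regional Nodal Irradiation), swelling that goes with marked weight gain or arm trauma is not counted, and swelling before or during radiotherapy is attributed to surgery. Skin and appearance have no parallel rule.

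**Working it through.** The plan states no figure to reproduce here. The check is arithmetic on the visit windows, then on the share of patients.

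**Inputs.** From the Protocol, Data Collection: late regular window, months 12 to 18 after XRT; first reconstruction visit within 1 month of surgery, side not stated; second visit 5 to 7 months after surgery; previous regular visit at 7–12 weeks. From the SAP, Data: 75 cases. Not in either document: the number reconstructed, and the timing of surgery. I take the SAP's 1-year value to be the 12–18 month visit, since the SAP gives no window of its own.

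**1. When is the 12–18 month value post-surgical?** Let surgery be at month s after XRT.
- If s is below 12, every assessment in the window follows surgery.
- If s is between 12 and 18, it depends on the visit date. Assuming visits are spread evenly over the window, the chance that the visit follows surgery is (18 − s)/6. At s = 13 this is 5/6 = 83%; at s = 15, 3/6 = 50%; at s = 18, 0%.
- If s is above 18, the value is unaffected.

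**2. When can one visit serve both purposes?**
- Second reconstruction visit: it can fall in the window when s + 7 ≥ 12 and s + 5 ≤ 18, so s is 5 to 13. It must fall there when s + 5 ≥ 12 and s + 7 ≤ 18, so s is 7 to 11.
- First reconstruction visit, either side of surgery: s + 1 ≥ 12 and s − 1 ≤ 18, so s is 11 to 19. If it is held only before surgery, s is 12 to 19.

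The two steps give different ranges. With s = 3, no reconstruction visit can be shared with the 12–18 month visit, yet that visit is post-surgical. With s = 16 and the first visit held before surgery, the visit can be shared and is free of any surgical effect.

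**3. Is a late pre-surgical value secured?** Twelve weeks is 84 days, and 84/30.4 = 2.8 months. No regular visit falls from about month 2.8 to month 12, a gap of about 9 months. The optional long-term assessment starts no earlier than 1 year and does not fill it. For surgery in this gap, the first reconstruction visit is the only scheduled chance of a later radiation-only value, and it may be held after the operation.

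**4. How many values?** With k affected patients among 75, the share is k/75:

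| k (assumed) | Share of 75 |
|---|---|
| 1 | 1.3% |
| 5 | 6.7% |
| 10 | 13.3% |
| 20 | 26.7% |

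The Protocol's accrual text mentions chest wall patients only in the nodal group, planned at 30 evaluable. If they sit only there, a rough ceiling is 30/75 = 40%. That is not certain, because Study Design allows chest wall treatment with or without nodal irradiation.

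For each unit by which reconstruction moves an outcome, the pooled mean moves by k/75 units: 0.07 at k = 5 and 0.27 at k = 20, if all 75 supply a value. The documents give no size for that effect.

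**The case against.** The strongest reply is that little depends on this. The outcomes are secondary in the Protocol, and pain and appearance are not among the SAP's outcomes. The acute Grade 3 skin monitoring, lymphedema and plexopathy outcomes are largely untouched. Surgical treatment is recorded, and the SAP has a multivariable regression, so adjustment is possible. The SAP is dated 04/01/2021 and written in the past tense, so new visit wording may change nothing already collected.

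Much of this stands and limits the weight of the point. It does not remove it. Reconstruction is not a named covariate, and selection by univariate significance does not ensure that it enters a model. Reach beyond secondary outcomes is possible but not shown: the primary cutaneous toxicity rate has no stated time point, and the nodal stopping rule refers to Grade 3 skin toxicity without limiting it to acute events.

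A reader might also infer stronger claims, which the documents do not support:
- *Shared visits cause the problem.* The overlap sentence only avoids duplicate visits. Steps 1 and 2 show that separate visits would not help when surgery precedes the assessment.
- *The late values measure surgery and not radiotherapy.* They reflect both, and the documents size neither.
- *All reconstructed patients are affected.* Surgery after the 12–18 month assessment leaves it clean.
- *No radiation-only measurement may exist.* For surgery after week 12, the values at fraction 15, 2–5 weeks and 7–12 weeks all precede it. What may be missing is a late one.

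**Conclusion.** The point holds in a limited form. For mastectomy patients reconstructed before their 12–18 month assessment, 1-year STRA and its change from baseline, and the pain and appearance ratings to 18 months, combine surgical and radiation effects. The Protocol anticipates the operation, the SAP has no rule for it, and the wording of the first reconstruction visit does not secure a late pre-surgical value.

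The size cannot be fixed from the documents. The range of 1.3% to 26.7% of 75 cases rests on an assumed 1 to 20 affected patients, and the direction of any bias is unknown. The conclusion also assumes that the 1-year value is the 12–18 month visit and that at least one patient was reconstructed before it. The outcomes concerned are mainly secondary, so this is a modest but worthwhile correction.

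**What to change.** 1. **Protocol, Data Collection.** Define the first reconstruction assessment as taking place within one month before surgery. For visits already held, record whether each was pre- or post-operative.
2. **SAP.** Use the surgery date to flag every assessment as before or after permanent reconstruction, and state how many patients were reconstructed before the 12–18 month assessment. Report 1-year STRA, its change from baseline, and the pain and appearance results with and without post-reconstruction values. List the post-reconstruction values separately.
3. **What not to do.** Pre-reconstruction values may be shown alongside time since XRT, but should not stand in as 1-year values. The Protocol's Preliminary Data section says that skin thickening peaks at the end of XRT and falls significantly by 6 weeks in patients on the traditional 6-week course. Carrying a 7–12 week value forward would replace a surgical distortion with a timing one.

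The cost is small: one clarified visit definition, one flag, a few lines of SAP text and no added visits. Surgical treatment is already recorded, so the flag may need no new data if that record includes the reconstruction date. The downside is somewhat fewer patients in the results that exclude reconstruction. Those results describe a selected group, which is why both sets should be shown.

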Furthermore, in the UK START study, post mastectomy patients were included as well as patients requiring regional nodal irradiation although only 15% of the enrolled patients were post-mastectomy patients and only 15% of the entire cohort needed regional nodal irradiation. Therefore, these patients at relatively higher risk for lymphedema/brachial plexopathy from XRT were under-represented in the UK START study. However, among the small number of patients treated with hypofractionated XRT to the regional lymph nodes (supraclavicular radiaton), there were no significant increases in lymphedema or brachial plexopathy compared to women treated with standard 5 weeks of XRT to the supraclavicular fossa.[6]

Additionally, a now standard boost dose to the lumpectomy cavity or chest wall, proven to significantly improve local control by 10% or greater in women less than 50 years of age [14-16], was not required in either arm of the Canadian or UK study. [4, 5] The boost dose has been shown to improve locoregional control in all patients by a minimum of 3% but appears to have the greatest impact in younger patients.[14-16] This boost dose has extended conventional XRT treatment from 5 (50 Gy in 25 fxns) to 6 weeks (60 Gy in 30 fxns) in the majority of patients treated within the United States.

At our institution, we have one of the largest experiences with simultaneous integrated boost (SIB) technique in patients with BrCA; we deliver 45 Gy in 25 fxns to the whole breast while treating the cavity simultaneously to a higher dose of 59.92 Gy in 25 fxns. Our published experience shows that at 3 years, our 5-week regimen is generally well tolerated with <1% of patients developing Grade 3 cutaneous toxicity and only 2.8% of patients recurring locally.[17] Our results are particularly important given that 39% of these patients were AA, 33% were premenopausal, 30% had breast separation >25cm, and 45% received chemotherapy, all factors associated with heightened skin toxicity from XRT. [17]

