### Secondary Outcome Measures:

- 1. Rate of cutaneous toxicity, as measured by changes in cutaneous measurements, acquired vis ultrasound tissue characterizations (UTC)
- 2. Local control will also be assessed through routine physical examination, annual screening mammograms, ultrasound, and biopsy to confirm local recurrence.
- Blood will be analyzed for biomarkers and inflammatory markers including(tumor necrosis factor (TNF)-alpha, soluble TNF receptor 2 (sTNFR2), interleukin (IL)-6, IL-1ra, and C - reactive protein (CRP) as well as genetic factors to determine if they are associated with development of cutaneous toxicity.
- 4. Change in Multidimensional Fatigue Inventory (MFI) Score

[Time Frame: Baseline, End of Follow Up (Up to 18 months)] [Safety Issue: No]

The Multidimensional Fatigue Inventory (MFI) is a 20-item self-report instrument designed to measure fatigue. Scores range from 20 to 100. The higher the score, the more fatigued.

5. Change in Pittsburgh Sleep Quality Index (PSQI) Score

[Time Frame: Baseline, End of Follow Up (Up to 18 months)] [Safety Issue: No]

The PSQI is a self-rated questionnaire which assesses sleep quality and disturbances over a 1-month time interval. Scores range from 0 to 21. A score of less than or equal to 5 is associated with good sleep quality. A score greater than 5 is associated with poor sleep quality.

6. Change in Perceived Stress Scale (PSS) Score

[Time Frame: Baseline, End of Follow Up (Up to 18 months)] [Safety Issue: No]

The PSS is a self-reported instrument used to measure the perception of stress. Scores range from 0 to 40. Score of 20 or higher are considered high stress.

7. Change in Patient Reported Outcomes Measurement Information System (PROMIS) Fatigue Short Form Score

[Time Frame: Baseline, End of Follow Up (Up to 18 months)] [Safety Issue: No]

The PROMIS Fatigue questionnaire is a self-report tool used to evaluate frequency, duration, and intensity of fatigue over the past seven days. Scores range from 7 to 35. The higher the score, the more fatigue.

8. Change in an Inventory of Depressive Symptomatology-Self Reported (IDS-SR) score

[Time Frame: Baseline, End of Follow Up (Up to 18 months)] [Safety Issue: No]

The IDS-SR is a self-reported measure in which participants rate the frequency of depression symptoms within the past seven days. Scores range from 0 to 84, with higher score reflecting greater severity of depressive symptoms.

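### After 18 months the plan gives no schedule or outside route for recurrence, the phone survey does not ask about it, and LRFS and DRFS end at the last Emory contact

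*Protocol*

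**What the plan says.** **Recurrence as an outcome.** Item 2 of the protocol's Secondary Outcome Measures reads "Local control will also be assessed through routine physical examination, annual screening mammograms, ultrasound, and biopsy to confirm local recurrence". The SAP, under Outcome and definition, adds two time-to-event endpoints: "Local Recurrence-free Survival (LRFS) was defined as months from the date of radiation ended to local recurrence or last seen at Emory" and "Distant Recurrence-free Survival (DRFS) was defined as months from the date of radiation ended to distant recurrence or last seen at Emory".

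**Contacts after treatment.** Under Data Collection, the last dated visit for all patients is at 12-18 months after radiotherapy. Some mastectomy patients have extra visits around reconstruction. A long-term in-person assessment between 1 and 10 years is optional. Then: "A follow up phone survey will be taken between 18 months and 10 years after treatment".

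**Content of the call.** In it "the patients will be asked to rate their fatigue level, breast pain, how happy they are with the look of their breast" and how different the two breasts are. The only disease-related item is "They will also be asked if they are on any hormonal treatment for breast cancer and if so, the date they started". Recurrence, metastasis and new cancer treatment are not on the list.

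**Other recording of recurrence.** The same section separately says that local control, distant metastasis and survival will be recorded as clinical outcomes. It names no source, timetable or end date.

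**The concern.** The trial plans to speak to patients up to 10 years after treatment, and it analyses recurrence-free survival. Yet the call collects nothing on recurrence, and the SAP's censoring date ignores it. If a patient moves her care elsewhere and relapses there, the trial can have her on the phone and still hold no record of the event.

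At stake are the number of late recurrences and the amount of follow-up behind LRFS and DRFS, and therefore how far these curves can be read beyond the scheduled visits. The toxicity rates listed under Primary Outcome Measure do not depend on this.

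**Working it through.** **Step 1. What each route provides after the 12-18 month visit.**

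| Route | Recurrence covered? | Schedule after 18 months | Recurrences diagnosed elsewhere |
|---|---|---|---|
| Clinical outcomes to be recorded (Data Collection) | Local control and distant metastasis | None stated | No route stated |
| Examination, mammograms, ultrasound, biopsy (Secondary Outcome Measures, item 2) | Local only | Mammograms annual; duration not stated | No route stated |
| Long-term visit (Data Collection) | No explicit item | Optional, 1-10 years | No route stated |
| Phone survey (Data Collection) | No | 18 months to 10 years | Could be asked, is not |

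The SAP does not say where a recurrence must be diagnosed to count. It does fix the censoring date at the last time seen at Emory.

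**Step 2. Is the long horizon real?** Data Collection provides for calling patients who completed the study before 9/24/2013, and the SAP is dated 04/01/2021. That is about 7.5 years, so for any such patients most of the potential follow-up lies beyond the last dated visit.

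**Step 3. Illustration of size.** The documents state no expected number of recurrences, no 10-year rate and no distribution of time to last contact, so there is no figure of the plan's own to reproduce.

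Inputs: "only 2.8% of patients recurring locally" at 3 years in the institution's own earlier series (Background), and 75 analysed cases (SAP, Data). Assumptions: a constant hazard carried to 10 years, and no deaths.

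- Hazard: λ = −ln(1 − 0.028)/3 = 0.00947 per year.
- Cumulative risk: F(t) = 1 − exp(−λt). Expected events: 75 × F(t).
- By 18 months: 1.06. By 3 years: 2.10. By 5 years: 3.47. By 7 years: 4.81. By 10 years: 6.77 (F = 9.0%).
- Share of 10-year events falling after a common last contact at time c: 1 − F(c)/F(10).

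| All patients last seen at | Share after last contact, constant hazard | Range, Weibull shape 0.5 to 1.25 through 2.8% at 3 years |
|---|---|---|
| 18 months | 1 − 1.06/6.77 = 84% | 61% to 90% |
| 3 years | 1 − 2.10/6.77 = 69% | 45% to 77% |
| 5 years | 1 − 3.47/6.77 = 49% | 29% to 56% |
| 7 years | 1 − 4.81/6.77 = 29% | 16% to 35% |

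The share passes 50% when the common last contact is before about 4.9 years (2.4 to 5.6 years across those shapes).

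Mixed follow-up: if a fraction q is seen to 10 years and the rest only to 18 months, the share is (1 − q) × 84.4%. That is 63% for q = 25%, 51% for q = 40% and 42% for q = 50%.

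The other rate in the Background, 1 of 91 patients at a median of 1 year in an earlier 15-fraction study, counts locoregional recurrence. Treated as a 1-year risk it gives λ = −ln(1 − 1/91) = 0.01105 per year and the same shares to the nearest percent. No distant recurrence rate is given, so DRFS cannot be sized.

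**Step 4. Loss or bias?** A patient censored at her last Emory visit adds no event-free time after it. Censoring alone therefore costs events and precision. Bias needs one of three further conditions:

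- Leaving Emory is related to recurrence.
- A recurrence treated elsewhere goes unreported in a patient later seen again at Emory, so that event-free time is credited wrongly.
- Outside recurrences are counted while event-free patients are still censored at their last Emory visit. This makes recurrence look too frequent.

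**The case against.** The strongest reply is that the call was never the instrument for recurrence. The protocol separately records local control and distant metastasis, and it follows local control by routine examination and annual mammograms. The 18-month time frame is attached to the questionnaire and rating outcomes, not to local control. The SAP counts a recurrence wherever it is diagnosed; only the censoring date mentions Emory. Local control is one of 15 secondary measures. The SAP is also written in the past tense, so new questions may come too late for these 75 cases.

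Much of this stands. It rules out three readings that a reader might infer:

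- *Recurrence is not collected after 18 months.* The documents do state an intention to collect it. What they lack is a schedule, a source and a route for outside diagnoses.
- *Most recurrences in the 10-year window will be missed.* This depends on when patients were last seen, which is not reported. The share runs from a clear majority to a minority.
- *LRFS and DRFS are biased upward.* Both the presence and the direction of bias depend on the conditions in Step 4. None of them is established.

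Nor do the documents plan a comparison with the 2.8%, which appears only as background.

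The reply does not close the gap. An intention to record does not say how a recurrence found elsewhere reaches the dataset, and no method at all is named for distant recurrence.

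**Conclusion.** The point holds as an inexpensive improvement to secondary endpoints. The plan reaches patients by phone up to 10 years after treatment but asks nothing about recurrence, and its censoring rule gives that contact no weight in LRFS or DRFS. The certain effect is lost late events and follow-up time.

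The size depends on the unreported time to last contact: under constant hazard, 84% of the 6.8 local recurrences expected by 10 years fall after last contact if all are last seen at 18 months, and 29% if all are last seen at 7 years. These figures rest on extrapolating a 3-year rate from an earlier 25-fraction series and only illustrate the scale. Bias is possible in either direction but not demonstrated. The primary toxicity conclusions are unaffected.

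**What to change.** **Protocol, Data Collection.** Add to the phone survey and the long-term visit a question on any local, regional or distant recurrence, with its date and place of treatment. Confirm positive answers from medical records.

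**SAP, Outcome and definition, items 5 and 6.** Count confirmed recurrences from any source. Censor event-free patients at the last date their recurrence status was known, whether from an Emory visit or from a phone contact at which it was asked. Make both changes together, since counting outside events alone would create the third bias in Step 4.

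**Reporting.** Give the distribution of time to last contact, and numbers at risk with the LRFS and DRFS curves.

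If the calls are already complete, make only the censoring and reporting changes. A past call that did not establish recurrence status should not extend follow-up.

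**Cost.** Two or three questions in a call already planned, record requests for the few patients who report a recurrence, and two lines of SAP text. The drawback is that self-reported recurrences and dates need confirmation.
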